1. LIST OF ABBREVIATIONS

AE	Adverse event
ALT	Alanine aminotransferase
AST	Aspartate aminotransferase
ANOVA	Analysis of variance
ATC	Anatomical Therapeutic Class
BQL	Below limit of quantitation
BUN	Blood urea nitrogen
CI	Confidence Interval
C _{max}	Maximum serum concentration
CFR	Code of Federal Regulations
CRF	Case report form
DVT	Deep vein thrombosis
EBV	Estimated blood volume
ECG	Electrocardiogram
FDA	Food and Drug Administration
FFP	Fresh frozen plasma
GCP	Good Clinical Practice
HBsAg	Hepatitis B surface antigen
Hct ₀	Hematocrit at -1 h before surgery
Hct _f	Hematocrit at 48 h after wound closure
Hct _{av}	Hematocrit average
HCV	Hepatitis C virus
IC	Informed consent
IRB	Institutional Review Board
MedDRA	Medical Dictionary for Regulatory Activities
mg	Milligram(s)
MI	Myocardial infarction
mL	Milliliter(s)
OTC	Over-the-counter
PK	Pharmacokinetic(s)
R	Reference formulation
T	Test formulation

RLD	Reference Listed Drug
RBC	Red blood cell
WBC	White blood cell
SAE	Serious adverse event
TEAE	Treatment-emergent adverse events
V _L	Volume of blood loss

3. PROTOCOL SYNOPSIS

Protocol Number and Title: CP-006-2017 – Efficacy and safety of tranexamic acid in spinal fusion surgery

Study Objectives: The primary objectives of this trial are to assess:

1. Total Blood Loss based on changes in hemoglobin (Blood loss will be calculated by Nadler's and Gross's formulae from the time of admission to hospital until discharge; Hemoglobin and hematocrit concentrations will be measured pre-operatively, post-operatively, and at 24 h and every 24h thereafter until discharge).
2. Incidence of autologous or allogenic blood transfusion, including red blood cells and coagulation components (such as fresh frozen plasma and platelets).

Secondary objectives include assessment of:

1. Total measured blood loss (measured intra-operatively and for up to 24 hours post-operatively and every 24 hours up to discharge when the two subfascial drains are removed). Total Blood Loss may be estimated as 3 times cell saver.
2. Number of patients with symptomatic anemia (such as tachycardia, hypotension, presyncope) of <8.0 g/dL hemoglobin, or any hemoglobin <7.0 g/dL, precipitated transfusion.
[Alternatively, allogenic blood transfusion will be considered for hemoglobin <9 g/dL intraoperatively or <8 g/dL post-operatively]
3. Number of patients with adverse events related to tranexamic acid such as confirmed deep vein thrombosis (DVT), pulmonary embolism (PE), or seizures.
4. Other outcomes will include functional recovery, duration of hospital stay, and wound

complications (infections, hematomas, and other complications related with surgery).

Number of Sites:	8
Principal Investigator and Study Site 1:	[name]. Clinical Professor of Surgery Cedars -Sinai Medical Center [name]
Principal Investigator and Study Site 2:	[name]. UCSF Spine Center [name]
Principal Investigator and Study Site 3:	[name]. Spine Care Orthopedics NYU Langone Medical Center [name]
Principal Investigator and Study Site 4:	[name]. FAAOS Massachusetts General Hospital Department of Orthopaedic Surgery [name]
Principal Investigator and Study Site 5:	[name]. Memorial Orthopaedic Surgery Group [name]
Principal Investigator and Study Site 6:	[name]. [name] PIs, [name]., Sub PI Division of Spine Surgery Rush University Medical Center Chicago IL

Principal Investigator and Study Site 7:	[name]. [name] Hobart, Tasmania
Principal Investigator and Study Site 8:	[name]. [name] Sydney, NSW
Clinical Laboratory:	
Institutional Review Board:	Western Institutional Review Board Research Foundation Address: [name] [contact]
Test and Reference Products:	Test Drug: Exela's Tranexamic Acid Solution for Injection (10 mg/mL), intravenous infusion bags, manufactured and provided by Exela Pharma Sciences, LLC from a single batch / lot will be administered to all randomized subjects. Placebo: Inactive ingredient mixture for injection without drug, intravenous infusion bags containing normal saline, manufactured and provided by Exela Pharma Sciences, LLC from a single batch / lot will be administered to all randomized subjects.
Study Design and Duration of Treatment:	This will be a multicenter, randomized, double-blind, parallel group study comparing tranexamic acid (test) to placebo (control) for reduction of perioperative blood loss after complex spinal fusion surgery (defined as T2 to Pelvis/Sacrum and greater than 4 Functional Spinal Units (4 discs/motion segments=5 Vertebral segments)). In addition to test and control treatments, all patients undergoing spinal fusion surgery will receive anesthesia and standard of care for blood loss including colloid/crystalloid fluid replacement and packed red

cells, if necessary, according to a common multi-institutional protocol. Anesthesia will keep the mean arterial pressure as low as safe for the patient during exposure of surgery (estimated at 60-80 MAP). Patients will be randomized to receive either 30 mg/kg tranexamic acid as a one hour infusion (3 mL/kg) loading dose prior to start of procedure and as an infusion at 3 mg/kg/h (0.3 mL/kg/h) of tranexamic acid throughout the surgery in the test group; or, a one hour infusion at 3 mL/kg of 0.9% saline prior to start of the procedure and an infusion of 0.9% saline at 0.3 mL/kg/h in the control group. The maximum total dose will be 50 mg/kg.

The active phase of the study will be until discharge postoperatively for efficacy measurements and at 6 weeks for safety follow-up. The randomization will be open only to the statistician generating the randomization sequence. All PI(s), study conduct and monitoring staff, as well as the subjects will be completely blinded to the treatments except in the case of emergency.

The study will be terminated if $\geq 5/12$ or $10/36$ patients enrolled in the study are diagnosed with treatment related serious adverse events.

**Study
Termination**

Phase:

This will be a Phase III study.

**Inclusion
Criteria:**

All adult patients over age eighteen electively undergoing complex spinal fusion surgery (T2 to Pelvis/Sacrum, greater than 4 FSU's (5 vertebral segments or more)) and have a negative serum pregnancy test result at screening, if female, will be eligible.

Exclusion Criteria:	Allergy to tranexamic acid; spinal tumor/intradural pathology; ankylosing spondylitis; acquired disturbance of color vision; pre-operative anemia (Hb <110 in females, Hb <120 in males); refusal of blood products (Jehova's witnesses); pre-operative use of anticoagulant therapy (Coumadin or heparin within 5 days of surgery); fibrinolytic disorders requiring intra-operative antifibrinolytic treatment; hematological disease (thromboembolic events, hemoglobinopathy, coagulopathy, or hemolytic disease); female patients using combination hormonal contraception; patients with history of subarachnoid hemorrhage; patients with serum creatinine levels above ULN
Population:	Up to approximately 150 patients will be enrolled.
Study Duration:	Approximately 2 months, including a screening visit, drug dosing during surgery, and a 6 week follow up.
Study Procedures:	
Subjects who meet admission criteria will be assigned sequential numbers beginning with site#-001. A completed subject is a subject who satisfies the admission criteria and who completes all required assessments. When the subjects meet admission criteria and provide written informed consent, they will receive a subject number and be randomized by subject number into one of two treatment arms. They will receive either tranexamic acid or normal saline according to the randomization schedule.
 
Preoperative Visit: Subjects will provide written informed consent and will then undergo pre-operative data collection/screening, including:
 
• Inclusion Exclusion criteria assessment• Diagnosis leading to surgery• Planned procedure

- Schwab Curve type and coronal curve magnitude (Cobb angle)
- Patient age and demography
- Height, Weight, and Body Mass Index
- Number of units of autologous blood donation
- CBC: Hb/Hct/WBC/platelet count (post-autologous donation)
- Coagulation Profile: PT/PTT/INR
- Medical History and Medication Use
- History of Previous Spine Surgery
- Drug / Alcohol / Tobacco Use
- Medication Allergies
- Pregnancy testing (females only)

Surgery, Drug Dosing, and Hospital Stay: Blinded treatments will be administered at an initial dose of 3 mL/kg as a 1-hour infusion using a calibrated infusion pump prior to start of procedure, and as a 0.3 mL/kg/h infusion throughout the surgery. Blood lost during surgery will be collected by subfascial Hemovac drains at the incision site into canisters containing heparinized saline. Volumes collected will be recorded post-surgery and every 24 h thereafter until discharge. Measured Blood Loss will be estimated as 3 times cell saver; estimates will be taken off of the anesthesia record.

The site will provide a person who will collect blood during consult in OR and record variables and measurements on the data collection sheet throughout the entire surgery. Final Measured Blood Loss will be determined post removal of the two subfascial hemovac drains placed during the procedure.

The Total Blood Loss will be estimated based on the hemoglobin content of the blood prior to surgery (mg/dL) and at each of the desired post-surgery time-points (mg/dL). Blood samples for hemoglobin measurement will be collected prior to start of procedure, at the end of the procedure, at 24 h, and every 24 h thereafter until discharge and removal two subfascial drains. Hematocrit analysis will also be conducted on all collected blood samples. The total amounts of fluids infused and amounts of any red blood cell transfusions may be considered, as applicable, in determining the changes in hemoglobin.

In addition, the following data will be recorded:

- Treatment ID
- Details of surgical procedure [Number of vertebrae fused, number of anchors used, and type of anchors used (screws, hooks, or anchors); Number and type of osteotomies performed]
- Any complication prolonging the surgery time or increasing patient blood loss
- Surgery time
- Estimated blood loss peri-operatively (from drainages and absorbent/surgical pads)
- Volume of cell saver delivered
- Units of autologous transfusion and allogenic transfusion
- Units of fresh frozen plasma and platelets administered
- Volume of crystalloids/colloids given

- Urine output
- Location of Hemovac drains and number of drains placed
- Drain output recorded daily
- Length of drain use (uniformly remove drains when output <120 mL/day)
- Length of hospital stay
- Complications of autologous or allogenic transfusion
- Complications of tranexamic acid including renal, hepatic, thromboembolic, and brain/CNS
- Functional recovery assessments will be completed prior to discharge
- Any wound complications for the duration of hospitalization

Follow-up Procedures: Follow-ups on wound complications will be completed minimally at 6 weeks after surgery. Follow-ups on adverse events related to tranexamic acid (such as seizures, DVTs, and PEs) will be reported immediately if they occur.

Adverse events (AEs) will also be monitored by the investigator and/or designated research staff and spontaneous reporting throughout the study.

Confinement: Patients will be confined to the clinic for surgical procedures and recovery as directed by the principal investigator

Study Endpoints: The primary endpoints of this trial are to assess:

1. Total Blood Loss based on changes in hemoglobin (Blood loss will be calculated by Nadler's and Gross's formulae from the time of admission to hospital until discharge; Hemoglobin and hematocrit concentrations will be measured pre-operatively, post-operatively, and at 24 h and every 24h thereafter until discharge).
2. Incidence of autologous or allogenic blood transfusion, including red blood cells and coagulation components (such as fresh frozen plasma and platelets).

The Secondary endpoints include assessment of:

1. Total Measured Blood Loss (measured intra-operatively and for up to 24 hours post-operatively and every 24 hours up to discharge when the two subfascial drains are removed). Total Measured Blood Loss will be estimated as 3 times cell saver.
2. Number of patients with symptomatic anemia (such as tachycardia, hypotension, presyncope) of <8.0 g/dL hemoglobin, or any hemoglobin <7.0 g/dL, precipitated transfusion.
[Alternatively, allogenic blood transfusion will be considered for hemoglobin <9 g/dL intraoperatively or <8 g/dL post-operatively]
3. Number of patients with adverse events related to tranexamic acid such as confirmed deep vein thrombosis (DVT), pulmonary embolism (PE), or seizures.
4. Other outcomes will include functional recovery, duration of hospital stay, and wound

complications (infections, hematomas, and other complications related with surgery).

**Safety
Assessments:**

Safety assessments will include monitoring of AEs, and functional recovery assessments, wound complications, length of hospital stay, blood loss, and transfusions.

**Statistical
Methods:**

The primary efficacy variables and continuous secondary efficacy variables will be analysed using Analysis of Covariance (ANCOVA) where one factor is treatment (TXA vs Placebo) and the other factor is Surgeon. The initial analysis will include the interaction between the two factors in order to assess the similarity of effects across surgeons. Significant interaction effects will occur if (for example), TXA works for some surgeons but not for others. The final efficacy analysis will remove the interaction term and control for overall differences between surgeons.

Adverse events will be categorized using MedDRA codes. The TXA and placebo groups will be compared using Fisher exact tests of the number of patients with each category of adverse events. The total number of reported adverse events will also be presented.

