4. SCHEDULE OF PROCEDURES

Evaluation Procedure	Screening Visit	Day of Surgery	Discharge	Safety Follow-ups			Study Exit or Early Withdrawal ⁸
				24 h	Every 24 h until discharge	6 weeks	
Informed Consent	X						
Inclusion/Exclusion Criteria	X						
Diagnosis leading to surgery	X						
Planned procedure	X						
Schwab Curve type and coronal curve magnitude (Cobb angle)	X						
Patient age and demography	X						
Medical/Medication Use History	X						
History of previous spine surgery	X						
Height, Weight, Body Mass Index	X						
Number of units of autologous blood donation	X						
CBC: Hb/Hct/WBC/platelet count (post-autologous blood donation)	X						
Coagulation Profile: PT/PTT/INR	X						
Pregnancy Tests ¹	X	X					
Serum Creatinine	X						
Drug / Alcohol /Tobacco Use	X						
Medication Allergies	X						
Physical Examination	X	X					X
Treatment ID		X					
Details of surgical procedure ²		X					
Surgical complications		X					
Surgery time		X					
Volume of cell saver delivered		X					

Blood Collection ³		X	X				
Location of Hemovac drains		X					
Length of drain use			X				
Length of hospital stay			X				
Peri-operative Blood Loss Assessments ⁴		X	X				
Transfusions ⁵		X					
Complications related to transfusions		X	X				
Urine output ⁶		X					
Tranexamic acid related complications ⁷		X	X	X	X	X	X
Functional recovery assessment		X	X	X	X	X	X
Wound Complications		X	X	X	X	X	X

¹ Females must have a negative serum pregnancy test result at screening and a negative urine test prior to surgery.

²Number of vertebrae fused, number of anchors used, and type of anchors used (screws, hooks, or anchors);
Number and type of osteotomies performed

³ Blood for Hb and Hct measurements will be collected pre-surgery, immediately post-surgery, at 24 h and every 24 thereafter until discharge.

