8.4. Randomization and Blinding

When the subjects meet admission criteria and provide written informed consent, they will receive a subject number and be randomized by subject number into one of two treatment arms. They will receive either tranexamic acid or normal saline according to the randomization schedule. The randomization schedule will be generated prior to study initiation by a statistical programmer. The pharmacy will perform and document the randomization.

Subjects will be treated according to a randomization schedule prepared prior to the start of the study. The investigator site personnel as well as Exela personnel involved in the monitoring or conducting of the trial will be blinded to the trial drug codes (or kit codes), except in the case of an emergency. Trial drug codes will not be available to the above personnel until after the completion of the trial and final data review.

An individual decoding unit containing emergency identification of the kit contents will be provided for each kit.

- i. This decoding unit must not be opened unless an actual emergency occurs. The investigator should also make a careful note of the date, time of opening, and the reason.
- ii. In the event that a decoding unit is opened, the Exela monitor must be notified immediately by the investigator.
- iii. At the conclusion of the trial, all decoding units are to be returned to Exela together with unused drug supplies.

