9.2.3. Preparation

Tranexamic Acid Injection (10 mg/mL) is suitable for direct administration and no additional preparation is necessary.

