11.2. Sample Size Determination

Assuming a two-sided alpha level of 0.05, 80% power and estimated mean blood loss of 2000 mL in the control group (with a relatively low estimated standard deviation of 1000 mL due to limitations in the type of surgery and the patient population) a 25% decrease in blood loss in the treated group would require 128 patients (64 per group). Thus, the proposed sample size of 150 patients (100 active and 50 placebo) will allow 14.7% loss to follow-up which should be sufficient considering the relatively small likelihood of loss to follow-up in these patients.

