11.3. Populations for Analysis

Up to approximately 150 patients will be enrolled.

The primary analysis population will be a modified Intent to Treat (mITT) population consisting of all subjects receiving an injection of TXA or Placebo.

The secondary analysis population will be a Per Protocol (PP) population consisting of all subjects without major protocol violations (to be

determined by a blinded committee prior to breaking the double-blind code).

The safety population will consist of all subjects receiving an injection of TXA or placebo.

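### Randomisation is tied to eligibility and consent rather than to dosing, so patients randomised but never dosed would use slots on the 100:50 list and drop out of the mITT, and the power margin at 2:1 is only about 6 to 8 patients.

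*Combined protocol and SAP*

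**What the plan says.** Section 3 (Protocol Synopsis, Study Procedures) provides that subjects who meet the admission criteria and "provide written informed consent, they will receive a subject number and be randomized by subject number". Section 8.4 repeats the rule: "they will receive a subject number and be randomized by subject number into one of two treatment arms". It adds that the pharmacy carries out and documents the randomisation. Neither section names a visit, date or time.

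The Section 4 schedule has no row for randomisation. Consent and the inclusion/exclusion check are ticked only at the Screening Visit. Treatment ID is an item recorded on the Day of Surgery. Footnote 1 says: "Females must have a negative serum pregnancy test result at screening and a negative urine test prior to surgery".

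Section 11.3 defines the primary analysis population as an mITT "consisting of all subjects receiving an injection of TXA or Placebo". Section 10.3.5 lets the sponsor choose whether to replace withdrawn subjects.

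On sample size, Section 11.2 begins: "Assuming a two-sided alpha level of 0.05, 80% power and estimated mean blood loss of 2000 mL in the control group". The assumed spread follows in parentheses: "with a relatively low estimated standard deviation of 1000 mL". It concludes that "a 25% decrease in blood loss in the treated group would require 128 patients (64 per group"), and that 150 patients (100 active, 50 placebo) leave room for 14.7% loss to follow-up.

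**The concern.** The rule starts from eligibility and consent, while the analysis set starts from dosing. Nothing in the plan ties the two together. If a site randomises once screening is passed, several things can still stop dosing:

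- The surgery is elective and can be postponed.
- The urine pregnancy test before surgery may be positive.
- Some exclusions are counted back from surgery or from the first study drug: anticoagulant use in the synopsis, and blood donation, loss or transfusion and other research participation in Section 8.3.2, items 11 and 14.

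A patient lost in this way has used a place on the 100:50 list and a place within the enrolment of approximately 150, and may have tied up a single-subject kit (Section 9.1.3), but contributes nothing to the mITT. Sections 3 and 9.1.1 speak of product being given to all randomised subjects, so the plan assumes that randomised and dosed are the same set. It does not make them so.

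At stake are some power, drift in the achieved 2:1 split, and a randomised set larger than the analysed set that the report must explain. With eight sites and no stated time, practice may also differ between sites.

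**Working it through.** **Inputs.** From Section 11.2: control mean 2000 mL; reduction 25%, so Δ = 0.25 × 2000 = 500 mL; SD σ = 1000 mL; two-sided α = 0.05; target power 80%. From Sections 5 and 11.2: 100 TXA and 50 placebo. The number randomised but not dosed is not in the documents, so it is varied.

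**Formula.** For a two-sample t-test with n1 and n2 patients, the noncentrality is δ = Δ / (σ√(1/n1 + 1/n2)), with n1 + n2 − 2 degrees of freedom. Power is the probability that a noncentral t variable exceeds the two-sided 5% critical value in absolute size.

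**The plan's own figure.** At 64/64, δ = 0.5/√(2/64) = 2.828 and power is 80.15%; at 63/63 it is 79.5%. So 128 is reproduced, for 1:1 allocation. The stated allowance is (150 − 128)/150 = 22/150 = 14.7%.

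**The same precision at 2:1.** Since 1/96 + 1/48 = 3/96 = 2/64, 96/48 has the same standard error as 64/64. At 2:1 the plan therefore needs about 144 patients, and the margin is 150 − 144 = 6, not 22.

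**Power as undosed patients accumulate, none replaced.**

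| Not dosed | TXA/placebo dosed | δ | Power |
|---|---|---|---|
| 0 | 100/50 | 2.887 | 81.8% |
| 3 (2%) | 98/49 | 2.858 | 81.0% |
| 6 (4%) | 96/48 | 2.828 | 80.2% |
| 7 | 95/48 | 2.824 | 80.07% |
| 7 | 96/47 | 2.809 | 79.7% |
| 8 | 95/47 | 2.804 | 79.5% |
| 9 | 94/47 | 2.799 | 79.4% |
| 15 (10%) | 90/45 | 2.739 | 77.6% |
| 22 (14.7%) | 85/43 | 2.672 | 75.5% |

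**Where 80% is crossed.** With seven losses the answer depends on how they fall: 95/48 is just above 80% and 96/47 just below. Over all possible splits of seven losses, power runs from 77.7% (all placebo) to 80.8% (all TXA). With whole patients split as near 2:1 as possible, the t-test first falls below 80% at eight losses. The normal approximation gives 82.3% at 100/50 and first falls below 80% at nine (94/47, 79.9%). Hence about 7 to 9.

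**Who leaves the mITT.** The one-hour loading infusion comes before the procedure (Sections 8.1 and 10.3.3), and the mITT needs only receipt of study drug. A patient whose operation is cancelled after the infusion has begun stays in. Only patients who receive no study drug are left out.

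**The case against.** The strongest reply is that the plan never says randomisation happens at screening. A reader might infer this from the schedule, but the documents do not support it as a stated fact. The trigger names no visit, Treatment ID is recorded on the day of surgery, and a pharmacy-run randomisation fits assignment at dispensing. Inclusion criterion 2 in Section 8.3.1 also requires a negative urine test at each admission, so a woman of childbearing potential has arguably not met the admission criteria until that test is done. All this stands, and the point must be that the time is not stated and not tied to dosing. It does not settle the matter. The urine test concerns only some patients, the synopsis inclusion criteria mention only the serum test, the eligibility check is ticked only at screening, and recording an identifier does not show when the arm was assigned.

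Three other tempting readings also go too far. One is that any cancelled operation removes a patient from the mITT; it does so only if no study drug was given. Another is that the seventh loss takes power below 80%; the 79.94% at 143 patients needs a fractional split of 95.3/47.7. The third is that the time of randomisation causes the thin margin; that comes mainly from sizing at 1:1 and allocating 2:1, and any kind of loss would expose it.

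Finally, losses can be replaced and the enrolment figure is approximate. That is true, but replacement is discretionary, is worded for withdrawn subjects, and does not say whether it covers patients never dosed or how a replacement is allocated.

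**Conclusion.** The concern holds in a limited form. The plan allows randomisation before the day of surgery, and a randomised patient who is never dosed drops out of the primary analysis. As long as the blind is intact, the decision not to dose cannot depend on the arm, so no bias is expected. The effect is on power and on the accounting of patients.

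The size is modest. Power starts at 81.8% and falls below 80% after about 7 to 9 undosed patients. An assumed undosed rate of 2% to 10% gives 81.0% to 77.6%. These figures rest on the plan's 500 mL difference and 1000 mL SD, on losses falling near 2:1, and on no replacement. The documents give no rate of undosed patients, so how many would occur is unknown. The gap between a real margin of about 6 to 8 patients and the stated 22 is a separate sizing matter, but it is why avoidable losses before dosing are worth preventing.

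**What to change.** In Sections 3 and 8.4, state that the subject number is given at screening for identification only. Have the pharmacy assign the next kit from the randomisation list on the day of surgery, after the pre-surgery eligibility checks the protocol already requires and just before the first infusion is dispensed. Count the 100 and 50 from that assignment. Add a randomisation entry to the Section 4 schedule on the Day of Surgery. In Section 11.3, require that any randomised but undosed patients be reported by arm. In Section 11.2, recompute the loss allowance for 2:1.

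The cost is protocol wording. The small downside is that the pharmacy must make the assignment on the morning of surgery. It already performs the randomisation, and Section 9.2.3 describes the product as "suitable for direct administration and no additional preparation is necessary", so no preparation time is added. No extra patients or procedures are needed.
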